- If prior blood cultures are positive, repeated post-baseline blood cultures should be collected on the day that the positive blood culture is detected
- Repeated respiratory specimens should be obtained only if clinically indicated

PK Assessments:

- Blood samples for PK analyses will be taken from all subjects at sites where PK sampling is possible on Day 3 at the following times:
 - Within 10 minutes before study drug administration
 - 2-4 h after study drug administration
 - subjects who have been hospitalized are also required to have a post-dose PK sample at 6-10 h (Day 3)

11.5 STUDY DAY 4

Administer study drug per the schedule in [Section 10.1](#).

Clinical Assessments:

- Record one set of vital signs, including body temperature (highest daily oral, rectal, or tympanic temperature), blood pressure, heart rate, respiratory rate, and pulse oximetry
- Perform a complete physical examination
- Assess CABP symptom severity ([Appendix III](#)). CABP symptom severity information entered into the eCRF will be used to programmatically determine clinical response at Day 4 ([Section 13.2.1](#)); note this is not an Investigator-determined clinical outcome.
- Identify, assess and record any AEs
- Record any concomitant medications

Microbiological Assessments:

- If prior blood cultures are positive, repeated post-baseline blood cultures should be collected on the day that the positive blood culture is detected
- Repeated respiratory specimens should be obtained only if clinically indicated

PK Assessments:

- A single blood sample for PK analyses will be taken from all subjects at sites where PK sampling is possible on Day 4 at 24-28 h following study drug administration on Day 3

11.6 STUDY DAY 5

Administer study drug per the schedule in [Section 10.1](#).

Clinical Assessments:

- Record one set of vital signs, including body temperature (highest daily oral, rectal, or tympanic temperature), blood pressure, heart rate, respiratory rate, and pulse oximetry
- Perform a complete physical examination
- Assess CABP symptom severity ([Appendix III](#))
- Obtain a 12-lead ECG
- Identify, assess and record any AEs
- Record any concomitant medications

Central Laboratory Assessments:

- Obtain hematology, coagulation and chemistry panel ([Appendix IV](#))

Microbiological Assessments:

- If prior blood cultures are positive, repeated post-baseline blood cultures should be collected on the day that the positive blood culture is detected

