13.2 CLINICAL OUTCOME ASSESSMENTS

13.2.1 Clinical Response at Day 4

The primary efficacy endpoint is clinical response (response, non-response, or indeterminate) at Day 4, tested in the ITT Population. Clinical response (response, non-response, or indeterminate) at Day 4 will also be tested in the micro-ITT Population as a secondary efficacy endpoint. Clinical response is determined programmatically using the Investigator's determination of CABP symptoms entered into the eCRF ([Table 13.2.1-1](#)). The Investigator is not responsible for categorizing subjects as clinical response, non-response, or indeterminate at Day 4. The severity of the subject CABP symptoms of dyspnea (shortness of breath), cough, production of purulent sputum, and pleuritic chest pain will be evaluated on a 4-point scale (absent, mild, moderate, or severe) based upon the CABP Symptom Severity Guidance in [Appendix III](#).

Table 13.2.1.-1. Clinical Outcome Assessment at Day 4.

Outcome	Definition
Clinical Response	Alive and programmatically-determined improvement of at least 1 level (e.g., severe to moderate, moderate to mild, mild to absent) in at least 2 CABP symptoms (dyspnea, cough, production of purulent sputum, and pleuritic chest pain) compared to Screening, without worsening in any other symptom. Severity of symptoms is based on a 4-point scale (absent, mild, moderate, or severe) (Appendix III).
Clinical Non-Response	Meets any of the following criteria: 
 • No programmatically-determined improvement of at least 1 level in at least 2 CABP symptoms compared to Screening

Table 13.2.1.-1. Clinical Outcome Assessment at Day 4.

Outcome	Definition
	
 Worsening in any of the 4 CABP symptoms compared to Screening Requires alternative rescue antibacterial therapy for CABP prior to Day 4 Death from any cause prior to Day 4
Indeterminate	Study data are missing for evaluation of efficacy at Day 4 for any reason, including lost to follow-up.

Abbreviations: CABP = community-acquired bacterial pneumonia.

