Improvement in CABP Symptoms and Normalization of Vital signs at Study Day 4	Meets all of the following criteria: 
 • Programmatically-determined improvement of at least 1 level in at least 2 CABP symptoms (dyspnea, cough, production of purulent sputum, and pleuritic chest pain) compared to Screening, without worsening in any other symptom (Appendix III) • Normalization of all vital signs: 
 ○ Temperature (oral, rectal, or tympanic) between 35.0°C and 38.0°C ○ SBP between 90 and 140 mm Hg, or return to baseline SBP \pm 5 mm Hg ○ Heart rate less than 100 beats per minute ○ Respiratory rate less than 20 breaths per minute ○ Oxygen saturation \geq 90% by pulse oximetry at room air • Ability to maintain oral intake • Normal mental status
No Improvement in CABP Symptoms and Normalization of Vital signs at Study Day 4	Does not meet all criteria for improvement in CABP symptoms and normalization in vital signs as defined above
Indeterminate	Study data are missing for evaluation of efficacy at Day 4 for any reason, including lost to follow-up.

Abbreviations: CABP = community-acquired bacterial pneumonia; SBP = systolic blood pressure.

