APPENDIX III CABP SYMPTOM SEVERITY GUIDANCE FOR INVESTIGATOR ASSESSMENT

CABP Symptom	Absent	Mild	Moderate	Severe
Dyspnea (Shortness of Breath [SOB])	No CABP-associated SOB; or return to pre-CABP baseline SOB	SOB with only strenuous activity but it does not interfere with subject’s usual daily activities; or mild SOB above pre-CABP baseline	SOB with usual activities and it does interfere with some of the subject’s usual daily activities; or moderate SOB above pre-CABP baseline	SOB with minimal exertion or at rest and it limits most of the subject’s usual daily activities; or severe SOB above pre-CABP baseline
Cough	Resolution of cough; or return to pre-CABP baseline cough	Cough present, infrequent, and it does not interfere with subject’s usual daily activities; or mild cough above pre-CABP baseline	Cough present, frequent, and it does interfere with some of the subject’s usual daily activities; or mild cough above pre-CABP baseline	Cough is present throughout the day and night; it limits most of the subjects’ usual daily activities and sleep patterns; or mild cough above pre-CABP baseline
Production of Purulent Sputum	No production of purulent sputum; or return to pre-CABP baseline productive cough	Production of small amount of purulent sputum; or minimal amount of sputum production above pre-CABP baseline	Production of moderate amount of purulent sputum; or moderate amount of sputum production above pre-CABP baseline	Production of large amount of purulent sputum; or large amount of sputum production above pre-CABP baseline
Pleuritic Chest Pain	No CABP-associated pleuritic chest pain	CABP-associated pleuritic chest pain present occasionally with deep breathing but it does not interfere with subject’s usual daily activities	CABP-associated pleuritic chest pain is present with normal breaths, and it does interfere with the subject’s usual daily activities	CABP-associated pleuritic chest pain is present at rest and/or with shallow breathing, and it limits most of the subject’s usual daily activities

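### Appendix III gives the same baseline-relative cough wording for Mild, Moderate and Severe, so cough grades feeding the primary Day 4 endpoint are ambiguous for subjects with a pre-existing cough

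*Combined protocol and SAP*

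**What the plan says.** Section 13.2.1 of the protocol has the investigator grade dyspnea, cough, purulent sputum and pleuritic chest pain. Each is to be "evaluated on a 4-point scale (absent, mild, moderate, or severe) based upon the CABP Symptom Severity Guidance" in Appendix III. Section 11.5 adds that "CABP symptom severity information entered into the eCRF will be used to programmatically determine clinical response at Day 4", and that the investigator does not decide the outcome.

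Under Table 13.2.1-1, Clinical Response needs a gain of one level or more in at least two of the four symptoms, with none worse. Clinical Non-Response includes "Worsening in any of the 4 CABP symptoms compared to Screening". The secondary endpoint in Table 13.2.3-1 uses the same grades: "Programmatically-determined improvement of at least 1 level in at least 2 CABP symptoms", plus normal vital signs, oral intake and mental status.

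In Appendix III, the Mild, Moderate and Severe cells for dyspnea, cough and sputum each give an absolute description and then, after an 'or', a change from the state before the pneumonia. In the cough row the Mild and Moderate cells both end "usual daily activities; or mild cough above pre-CABP baseline", and the Severe cell ends "usual daily activities and sleep patterns; or mild cough above pre-CABP baseline". In the Moderate column the other two rows read "or moderate SOB above pre-CABP baseline" for dyspnea and "or moderate amount of sputum production above pre-CABP baseline" for sputum.

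**The concern.** The baseline-relative clause is there for subjects who coughed before the pneumonia. For them it no longer separates the grades. A mild increase over the usual cough satisfies Mild, Moderate and Severe at once, while a moderate or severe increase matches no baseline-relative clause.

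Such subjects can enter. Inclusion criterion 3a (Section 9.2) accepts worsening as well as new symptoms, and exclusion criterion 7 (Section 9.3) removes only the severe form of COPD. The Absent cell for cough itself allows a return to the pre-pneumonia cough, so the table was written with these subjects in mind.

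Because response is computed from the recorded grades, no later clinical judgement can correct a wrong one. With some 40 to 50 centers planned, sites may also resolve the wording differently.

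**Working it through.** **1. The three rows side by side (clause after the 'or', paraphrased)**

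| Row | Mild | Moderate | Severe |
|---|---|---|---|
| Dyspnea | mild increase | moderate increase | severe increase |
| Purulent sputum | minimal increase | moderate increase | large increase |
| Cough | mild increase | mild increase | mild increase |

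Pleuritic chest pain has no baseline-relative clause. Each cough cell is otherwise complete and distinct in frequency and interference, so a text-extraction fault is unlikely. No other section corrects the wording, gives a separate cough scale, or says which alternative prevails.

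**2. How one grade decides the outcome**

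Take a subject with dyspnea Moderate and cough Moderate at Screening and the other two symptoms absent. On Day 4 dyspnea is Mild, and the cough is mildly above its usual level.

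- Cough graded Mild: two improvements, none worse, so Response.
- Cough graded Moderate: one improvement, so Non-Response.
- Cough graded Severe: one improvement and one worsening, so Non-Response.

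All three grades are open under the clause as printed. If sputum had also improved, grading the cough Moderate would still give Response, but Severe would not, because of the worsening rule.

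**3. The plan's own figure**

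Section 16.2.1 gives a 95% interval of 66.9% to 86.7% for a 78% response rate with 75 subjects. The Clopper-Pearson limits with n = 75 and x = 0.78 × 75 = 58.5 are 66.94% and 86.75%, which match within rounding. The wording defect does not alter this interval.

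**4. Illustration of size (all inputs assumed except the 78%)**

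The documents give no share of subjects with pre-existing cough, no severity mix and no mis-grading rate. The assumed inputs, chosen to reproduce 78%, are:

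- Screening probabilities for Absent/Mild/Moderate/Severe: dyspnea .10/.25/.45/.20, cough .03/.20/.50/.27, sputum .20/.25/.40/.15, pleuritic pain .35/.25/.30/.10.
- Day 4 change, independent per symptom: one level worse 1%, none 30%, one better 49%, two better 20%, truncated to the scale.
- Only subjects with at least two symptoms present are counted.

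Exact enumeration under the Table 13.2.1-1 symptom rule gives 78.02% response. Overall shift = share affected × shift among those affected. Subjects per arm = 75 × shift.

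| Assumed mis-grading of cough | Shift among affected (points) | 10% share | 30% share | Subjects per 75 |
|---|---|---|---|---|
| Truly Mild graded up, both visits, rate 10% | −1.71 | −0.17 | −0.51 | 0.13 to 0.38 |
| Same, rate 20% | −3.40 | −0.34 | −1.02 | 0.26 to 0.76 |
| Any non-absent grade, either direction, both visits, rate 10% | −3.61 | −0.36 | −1.08 | 0.27 to 0.81 |
| Same, rate 20% | −6.97 | −0.70 | −2.09 | 0.52 to 1.57 |
| Truly Mild graded up at Screening only, rate 10% | +0.22 | +0.02 | +0.06 | under 0.1 |
| Same, rate 20% | +0.43 | +0.04 | +0.13 | 0.03 to 0.10 |
| Every truly Mild Day 4 cough coded Severe (implausible) | −27.1 | −2.71 | −8.13 | 2.0 to 6.1 |

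A cruder sum makes the same point. With a 5–20% share, of whom 10–50% change Day 4 status in one direction, the rate moves by 0.05 × 0.10 = 0.5 to 0.20 × 0.50 = 10 points. The answer is set by the assumptions. The enumeration also draws errors at the two visits independently; a rater who applies one consistent reading would make correlated errors, which is not modelled.

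**The case against.** The best defence is that the intended reading is plain from the table. Every cell sits under a severity heading, and each cough cell opens with its own frequency and interference description. To record Severe for a mild increase, an investigator would have to disregard both. The appendix is guidance, and grading remains the investigator's judgement. Several chronic-cough conditions are excluded, including bronchiectasis, cystic fibrosis pneumonia and severe COPD. Grading is double-blind (Section 10.6), and Section 16.2 plans no formal comparison. Site training and manuals, which are not part of these documents, may carry the right wording.

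Most of this stands, and it keeps the weight low. The grading is ambiguous for a subgroup, not impossible, and blinding should keep errors from favouring an arm. It does not remove the defect. Unseen training material cannot correct the protocol text, and the printed clause still offers three grades for one state. Section 16.2.3.1 also reports a treatment difference with a 95% interval, and Section 16.2.1 says the data will inform the design of later studies. Avoidable noise in the Day 4 rate therefore has some cost.

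The criticism that the size estimate rests on assumptions is correct. The finding rests on the wording alone.

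**Conclusion.** The concern holds. The cough row of Appendix III is wrong as written, and the parallel rows show what was almost certainly meant. The table is the measuring instrument for the primary efficacy endpoint, so this is more than a cosmetic slip and should be corrected.

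The likely effect is small. Under the milder assumptions above, the response rate falls by 0.2–1.0 points, or 0.1–0.8 subject per arm of 75. Broader mis-grading gives a fall of 0.4–2.1 points, and errors at Screening only give a slight rise. None of these is a bound. Confidence is high in the wording defect; no effect size can be derived from the documents.

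**What to change.** Bring the cough row into line with the dyspnea row: the second alternative should refer to a moderate increase over the pre-pneumonia cough under Moderate and a severe increase under Severe. Notify sites and confirm which wording they have been using, including any eCRF labels or training material.

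If enrolment has begun, leave recorded grades unchanged and record which wording applied to each subject. An optional descriptive check is the Day 4 response with and without subjects whose medical history (Section 11.1) lists a chronic cough condition. It is a weak proxy, because that history has no specific item for cough before the pneumonia, and it can be omitted without affecting the core fix.

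The cost is two words in an appendix, carried in a protocol amendment. That needs sponsor approval (Section 17.1) and ethics and regulatory approval before use (Section 18.4), plus a site notice. No extra visits, samples or subjects are needed.

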APPENDIX IV SAFETY LABORATORY TESTS CONDUCTED BY THE CENTRAL LABORATORY

Hematology:
 
 • Hemoglobin • Hematocrit • Erythrocyte count • Mean red blood cell volume • Mean red blood cell hemoglobin • Mean red blood cell hemoglobin concentration • Leukocyte count (WBC) • Neutrophils (including immature neutrophils [bands] and absolute neutrophil count) • Lymphocytes • Monocytes • Eosinophils • Basophils • Platelets • Reticulocytes 
Coagulation:
 
 • Prothrombin time/International normalized ratio (PT/INR) • Partial thromboplastin time 
Urinalysis (only if local urine dipstick test abnormal and deemed clinically significant by the Investigator; see Section 11.1):
 
 • Specific gravity • pH • Protein • Glucose • Ketones • Bilirubin • Occult blood • Nitrites • Urobilinogen • Leukocyte esterase 	
Chemistry (Serum Concentrations):
 
 • Glucose • Calcium • Albumin • Total protein • Sodium • Potassium • Carbon dioxide • Chloride • Blood urea nitrogen (BUN) • Creatinine • Alkaline phosphatase • Alanine aminotransferase (ALT) • Aspartate aminotransferase (AST) • Total and direct bilirubin • Magnesium • Lactate dehydrogenase (LDH) • Phosphorus • Uric acid • Creatine kinase • Gamma-glutamyl transferase (GGT) • β-Human chorionic gonadotropin (β-HCG) for females
---	--

**APPENDIX V ORAL MOXIFLOXACIN SUMMARY OF PRODUCT
CHARACTERISTICS**

Insert SPC from Bayer plc, updated 26-August-2015,
<http://www.medicines.org.uk/emc/print-document?documentId=11841>

NDA 021085 AVELOX FDA Approved 8 May 2015 - Merck
https://www.merck.com/product/usa/pi_circulars/a/avelox/avelox_pi.pdf

